4.2.2 Handling of Withdrawals

Subjects are free to withdraw from the study or study treatment at any time. Subject participation in the study may be stopped at any time at the discretion of the Investigator or at the request of the Sponsor.

Subjects who discontinue study treatment or active participation in the study will no longer receive study drug. When a subject withdraws from the study, the reason(s) for withdrawal shall be recorded by the Investigator on the relevant page of the electronic case report form (eCRF). Whenever possible, all subjects who discontinue study treatment or withdraw from the study prematurely will undergo all end-of-study assessments at the time of ET. Subjects who fail to return for final assessments will be contacted by the site in an attempt to have them comply with the protocol. Methods for follow up will consist of 2 documented phone calls followed by 1 registered letter.

It is vital to obtain follow-up data on any subject withdrawn because of an AE or SAE. In every case, efforts must be made to undertake protocol-specified, safety, follow-up procedures.

4.2.3 Replacements

If the Investigator withdraws a subject for a reason related to the study drug (in the opinion of the Investigator), then the subject is considered discontinued from the study. Discontinued subjects will be replaced if deemed necessary by the Sponsor.

If a subject does not complete the study for a reason that is unrelated to the study drug, the subject may be replaced if the Sponsor instructs the site to do so. The decision regarding the replacement of subjects will be documented.

5 STUDY TREATMENTS

5.1 Method of Assigning Subjects to Treatment Groups

Each subject will be assigned a screening number. Once enrolled into the study, subjects will be assigned a unique subject number starting with a 2 digit site number, followed by a unique 2 digit subject number.

Subjects who replace discontinuing subjects after the first study drug administration has taken place will be assigned their own unique subject number and same cohort assignment as the subject being replaced.

5.2 Blinding and Randomization

This is an open-label study and no blinding procedures will be used. Following enrollment, subjects will be centrally assigned to one of 4 cohorts depending on CKD status (Table 5-1) and based on a predetermined algorithm. The 200 mg BID dose cohorts will be enrolled first. At least 2 males or females will be included in the 8 subjects (i.e., can be up to a 25%/75% split of male/female or 75%/25% split of male/female) assigned to each cohort. Similarly, at least 2 subjects with CKD1 or CKD2 will be included in 8 subjects each assigned to Cohorts 1 and 3.

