2.2.2 Secondary Endpoints

The effect of lixivaptan on urine osmolality by lixivaptan will be determined through evaluation of:

- Spot urine osmolality and 24h urine output.

The pharmacodynamic effects of lixivaptan will be determined through evaluation of:

- Serum creatinine, blood urea nitrogen (BUN), and estimated glomerular filtration rate (eGFR);
- Total kidney volume (TKV) and liver volume (LV) measured by abdominal magnetic resonance imaging (MRI); and
- Plasma copeptin, as a marker for circulating vasopressin.

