3.1.1 Rationale of Study Design

The I/E criteria in Section [4.1](#) were chosen to recruit an adequate number of subjects representative of the ADPKD population to achieve the study's primary objectives as presented in Section [2.1.1](#).

Based on existing clinical evidence with lixivaptan and the related vasopressin antagonist tolvaptan, the PK and PD properties of lixivaptan are not expected to differ in ADPKD subjects with CKD1 and CKD2 stages, therefore these subjects with relatively preserved kidney function will be combined into one study group. This approach decreases the total number of subjects that need to be recruited without compromising the study objectives. Conversely, subjects with moderately impaired renal function (CKD3 stage) may show distinct PK and PD responses to lixivaptan and will be enrolled into a separate group.

The PK profile of lixivaptan and its metabolites will be monitored for 3-5 half-lives after the last dose to define terminal PK parameters. Therefore, PK blood draws are included up to 96 hours, i.e. approximately 4 half-lives of the longest-lived metabolite of lixivaptan, after the last dose of lixivaptan (Day 7 PM).

Treatment with lixivaptan is associated with transient and reversible increases in serum creatinine and circulating vasopressin. In addition, based on clinical evidence with the related vasopressin antagonist tolvaptan,¹² lixivaptan may be associated with transient and reversible decreases in Total Kidney Volume (TKV). In order to characterize the time course and magnitude of these pharmacodynamic effects of lixivaptan in ADPKD subjects, the study design includes measurements of serum creatinine, plasma copeptin as a marker for circulating vasopressin, and TKV at three time points: at baseline, after completion of the scheduled treatment period and 4 weeks after the last dose of lixivaptan.

The sample size of 32 subjects in total, with 16 subjects per Cohort, is typical for this type of study and is considered adequate to meet the study objectives.

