6.1.6 MRI Assessment

In order to investigate lixivaptan's pharmacodynamic effect on kidney and liver volume, patients will undergo a standardized abdominal MRI assessment without use of intravenous contrast for the determination of combined renal volume of both kidneys (total kidney volume or TKV) and liver volume (LV) at 3 timepoints as specified in [Table 12-1](#):

- 1) at baseline (any time from Screening until CRU admission);
- 2) immediately after completion of the 7-day treatment period (Day 8 or 9); and
- 3) at the final End of Study assessment (Day 35 ± 2).

Given the importance of performing the second MRI assessment within a short time interval after the last dose of study medication (PM dose on Day 7), it is recommended that all MRI assessments be scheduled for each subject at the time of the Screening visit. Assessment windows are presented in [Table 12-2](#).

Occasionally, patients may be unable to continue into the study after completing their Screening visit and baseline MRI assessment (for example, due to changed personal circumstances or for not meeting laboratory inclusion criteria). These patients may subsequently qualify for the study and be rescreened at a later time. In this case, their prior baseline MRI assessment may be used instead of obtaining a new baseline MRI scan;

provided, however, that no more than 8 weeks have elapsed from the time of the initial MRI assessment until admission into the CRU.

The MRI acquisition protocol will be detailed in the study imaging manual. MRI images will be sent to a central reading facility for quality control and measurement of TKV and LV. Depending on technical feasibility, combined renal cyst volume (total cyst volume of both kidneys) and combined renal parenchyma volume (total parenchyma volume of both kidneys) may be determined for a subset of subjects at a later date.

In the absence of sonography or radiography evidence at the time of the Screening visit, the baseline MRI assessment could be used to confirm a subject's diagnosis of ADPKD according to modified Ravine criteria.

Subjects with ferro-magnetic prostheses, aneurysm clips, severe claustrophobia or other contraindications or exclusions interfering with MRI measurements will be excused from this procedure, but may participate in the study providing that all other eligibility criteria are met. Investigator should seek MRI safety guidance from local MRI facility.

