7.7.2 Pharmacodynamic Analyses

The change from baseline in urine osmolality, serum creatinine, plasma copeptin, TKV and LV after multiple doses of lixivaptan will be summarized by renal function group (CDK1/2 and CDK3), and at each scheduled time point using descriptive statistics (n, mean, SD, median, minimum, and maximum).

Except for the case of urine osmolality, the baseline value is the last value observed prior to first administration of study drug and any values after first administration of study drug are regarded as post-baseline values. The change-from-baseline variables will be calculated as the post-baseline value minus the value at baseline.

For urine osmolality assessments, the baseline value for each time point after first administration of study drug is the value observed at the corresponding time point on Day -1 (or Day 1 for the AM predose assessment only). Any values after first administration of

study drug are regarded as post-baseline values. The change-from-baseline variables will be calculated as the post-baseline value minus the value at baseline. The number of subjects who show suppressed urine osmolality, defined as spot urine osmolality < 300 mOsm/kg for 24h, on Day 1 (AM predose) compared with Day 8 (AM predose) will be determined.

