### 15. PHARMACODYNAMIC ANALYSIS

### 15.1. PHARMACODYNAMIC ENDPOINTS

The following are PD endpoints:

- Urine osmolality
- Specific gravity by refractometer
- Specific gravity by dipstick
- (24-hour) urine output
- (24-hour) fluid intake
- Fluid balance
- Total kidney volume (TKV)
- Liver volume (LV)
- Plasma copeptin
- Estimated glomerular filtration rate (eGFR); calculated by the 2009 Chronic Kidney
   Disease Epidemiology Collaboration (CKD-EPI) equation presented in Appendix 1 of the protocol.

A listing of all PD sample collection times will be provided. Subject listings of all PD data will be

Document: PK/PD STATISTICAL ANALYSIS PLAN

Author: [name] Version Number: 1.0

Version Date: 12 Aug 2019

Template No: CS\_TP\_BS016 - Revision 5 Reference: CS\_WI\_BS005

Effective Date: 01Apr2018

Palladio BiosciencesInsert Customer Name/Logo PK/PD STATISTICAL ANALYSIS PLAN: PROTOCOL PA-102 Page 34 of 39

presented for the observed values and change from baseline, based on the Safety Analysis Set. The observed value and the change from baseline in the PD endpoints will be summarized by cohort (renal function/CKD stage/dose), Study Day, dosing interval, and/or at each scheduled time point, as applicable, using descriptive statistics as described in Section 6.1 and Section 8. Additional summarization will be made with further stratification CKD stage within cohort. Pharmacodynamic summaries will be based on the PD Analysis Set. Any BLQ concentrations will be treated as 1/2 × LLOQ for the computation of change from baseline and descriptive statistics.

Any values after first administration of study drug are regarded as post-baseline values. Except for urine osmolality, the baseline value is the last value observed prior to first administration of study drug. For urine osmolality assessments, the baseline value for each time point after first administration of study drug is the value observed at the corresponding time point on Day -1 (or Day 1 for the AM predose assessment only).

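### The plan does not mask the central MRI reader, so TKV and liver volume may be measured with visit and dose known, in a study with no untreated arm

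*Protocol*

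**What the plan says.** Protocol 5.2 (Blinding and Randomization) says: "This is an open-label study and no blinding procedures will be used". It makes no exception for people who measure outcomes.

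Protocol 6.1.6 (MRI Assessment) schedules three scans per subject: baseline, end of dosing and end of study. On measurement it says: "MRI images will be sent to a central reading facility for quality control and measurement of TKV and LV". Masking and read order are not mentioned. A separate manual is cited, but for image acquisition: "The MRI acquisition protocol will be detailed in the study imaging manual".

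TKV and LV are secondary endpoints (2.2.2). Section 3.1.1 gives the direction thought possible for TKV, drawing on evidence from tolvaptan: "lixivaptan may be associated with transient and reversible decreases in Total Kidney Volume (TKV". It names no direction for LV and no size for either organ.

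The analysis is a within-subject difference. Protocol 7.7.2: "The change-from-baseline variables will be calculated as the post-baseline value minus the value at baseline". PK/PD SAP 15.1: "The observed value and the change from baseline in the PD endpoints will be summarized by cohort". PK/PD SAP 15.2 also plots TKV and LV against Day 7 AUC(0-14). Table 5-1 of the protocol has four cohorts, all on lixivaptan, and 5.2 has the 200 mg cohorts enrolled first. Neither SAP mentions masking of image reading.

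**The concern.** Open-label dosing does not require open-label image reading. Measuring an organ volume on MRI involves judgement, and the central reader need not know which visit or dose a scan belongs to.

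TKV is the exposed endpoint because the protocol states in advance which way it may move. A reader who knew the visit would know which scan might be expected to be smaller and which might be expected to recover. Expectation could then contribute to both halves of the pattern the study sets out to describe, the fall on treatment and the later return. With no placebo or untreated arm, nothing subtracts such a tendency. If the reader also knew the dose, a tendency that differed between 50 mg and 200 mg could look like a relation between exposure and volume in the PK/PD plots.

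**Working it through.** **Is masking provided anywhere?**

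- Protocol 5.2: no blinding procedures, without qualification.
- Protocol 6.1.6: central measurement; silent on masking and read order.
- Imaging manual: cited for acquisition only, and not among the documents.
- Non-PK/PD SAP and PK/PD SAP: silent.

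Central reading removes differences between site readers. It does not by itself remove knowledge of visit or dose. As written, the plan permits reads with both known.

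**Where would a reading tendency go?** Let r0, r1 and r2 be the average reading error at baseline, end of dosing and end of study. For one subject:

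- end-of-dosing change = true change + (r1 − r0) + random error
- end-of-study change = true change + (r2 − r0) + random error

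Write b = r1 − r0. The expected mean change over n subjects is the true change plus b, for any n. The random part has standard error SD/√n, where SD is the standard deviation of the within-subject change. So b keeps its full size while the random error around it shrinks. If r2 is close to r0, the reading error also mimics the return after dosing.

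For a comparison of doses, what remains is b(200) − b(50). That is zero if the tendency is the same at both doses and non-zero if it depends on a known dose.

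**Illustration.** The plan has no figure of its own to reproduce here: it gives neither a reading error nor an SD of change for TKV or LV, and the precision figures in protocol 7.4 concern only Cmax, AUC and adverse-event probabilities. The inputs below are therefore assumptions: true change zero, and b equal to 0.25, 0.5 or 1.0 SD. The sample sizes are 8 (one cohort), 16 (two cohorts) and 32 (all subjects). A two-sided 95% t interval excludes zero with the probability that a noncentral t variable, with n − 1 degrees of freedom and noncentrality b√n, falls outside ± the 97.5% t quantile. At b = 0.5 the noncentrality is 0.5 × √8 = 1.41 for n = 8 and 0.5 × √32 = 2.83 for n = 32.

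| b (SD of change) | n = 8 | n = 16 | n = 32 |
|---|---|---|---|
| 0.25 | 9.4% | 15.5% | 27.8% |
| 0.5 | 23.2% | 46.5% | 78.2% |
| 1.0 | 68.1% | 96.2% | about 100% |

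Without a shift every cell would be 5%. The plan specifies no confidence intervals for TKV or LV, so the table shows only how pooling subjects makes a reading shift look more convincing. It is not an error rate of a planned analysis.

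**The case against.** The strongest reply is that 5.2 sits in the chapter on study treatments and continues directly with cohort assignment, so its natural subject is blinding of the drug. Image reading belongs to 6.1.6, which is silent and prohibits nothing. This stands. A reader might infer that the protocol bans masked image reading; the documents support only that masking is not required. The imaging manual might contain reading instructions. If it does require masking, the unqualified sentence in 5.2 conflicts with it and still needs narrowing.

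A reader might also infer that the central reader knows which scan is which. No passage says that the facility receives visit labels, dose or cohort, or that scans are read as they arrive. The subject number in 5.1 consists of a site number and a subject number, with no cohort code. Scan dates could show the order, and enrolling the 200 mg cohorts first could hint at the dose, but these are possibilities rather than facts in the documents.

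It is tempting to express the bias as a share of the drug effect. A shift of 0.5% to 2% against a true change of 2% to 4% gives 0.5/4 = 12.5% to 2/2 = 100%. Both ranges are assumptions and the documents supply neither, so the ratio is not evidence that the bias is material. Nor do they say that the expected change is small, or that a TKV decrease reverses by four weeks; they only schedule a measurement then. Extending the expectation argument to LV is likewise unsupported, because no direction is stated for it.

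Finally, TKV and LV are secondary and summarized descriptively. No test, decision rule or sample size rests on them, and a tendency common to both doses cancels in a dose comparison. All of this limits the consequence. It does not help the planned change-from-baseline summaries, where nothing cancels.

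**Conclusion.** The point holds as a gap in the design of the TKV and LV measurement: the plan permits reading with visit, scan order, dose and cohort known, for a change from baseline that has no untreated comparison. A visit-dependent tendency would enter the TKV change in full at any sample size, and a dose-dependent one could distort the TKV and LV plots against exposure.

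The size is unknown. The percentages in the table rest on an assumed shift and on intervals that are not planned. The expectation argument applies to TKV; masking LV as well is for consistency, since both come from the same scans. The primary safety and PK objectives are untouched. This is an inexpensive improvement to a secondary endpoint, not a flaw in the main conclusions.

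**What to change.** In protocol 5.2, limit the statement to the drug: *there is no blinding of study drug.*

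In 6.1.6, add: *The central reader measures TKV and LV with visit date, visit label, dose and cohort removed, and with each subject's scans presented in random order. Quality control at receipt, and any cyst count for the Ravine diagnosis, are done by existing site or facility staff outside the masked volume read.* If the imaging manual already requires this, 6.1.6 should cite it for reading as well as for acquisition.

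The cost is administrative: removing identifying information and setting a read order. Dosing, scans and facility are unchanged. The facility must keep the volume reader apart from the labelled baseline scan when quality control or a cyst count is needed early, which is a matter of assigning existing staff. The one real downside is that final TKV and LV values become available only after a subject's last scan. Little depends on having them sooner: no TKV or LV value governs dosing or eligibility, the Non-PK/PD SAP plans no interim analysis, and the dry run in PK/PD SAP 4.2 serves programming only.

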- For subjects with family history of ADPKD, a minimum of 3 cysts per kidney by sonography or 5 cysts by computerized tomography (CT) or magnetic resonance imaging (MRI); or
- For subjects without family history of ADPKD, a minimum of 10 cysts per kidney by any radiologic method and exclusion of other cystic kidney diseases.

Subjects may be enrolled if they meet the modified Pei-Ravine criteria, have a confirmed CKD Classification of CKD1, CKD2 or CKD3 (Table 3-1 and see Appendix 1), and meet the other inclusion/exclusion (I/E) criteria (Section 4.1).

Table 3-1 Chronic Kidney Disease Classification Summary

CKD Classification	Cohorts	N	eGFR*
CKD1 or CKD2**	1 and 3	16 (8 per cohort)	eGFR \geq 60 mL/min/1.73 m ²
CKD3	2 and 4	16 (8 per cohort)	eGFR \geq 30 to < 60 mL/min/1.73 m ²

Abbreviations: CKD = chronic kidney disease, eGFR = estimated glomerular filtration rate, N = number of subjects.

*eGFR is calculated by the 2009 Chronic Kidney Disease Epidemiology Collaboration (CKD-EPI) equation ([Appendix 1](#)).

**At least 2 subjects with CKD1 or CKD2 will be included in 8 subjects assigned to Cohorts 1 and 3.

Subjects may be allowed to re-screen or have repeat testing after agreement between the investigator and medical monitor. Lab tests that need to be repeated during Screening may be obtained through the services of an at-home nursing service provided by the Sponsor.

Subjects who withdraw early from the study may be replaced at the discretion of the Investigator and of the Sponsor to ensure that approximately 32 subjects (8 subjects in CKD1/2 and 8 subjects in CKD3 per dose level, see [Table 5-1](#)) complete the study.

Study assessments including PK blood sampling, urine collection, PD blood sampling, physical examination findings, vital signs, ECGs, clinical laboratory tests, and monitoring of AEs will be performed at the timepoints presented in [Table 12-1](#). Adverse events and serious AEs (SAE) that are related to study participation (e.g., protocol-mandated intervention) will be recorded from the time the subject signs the Informed Consent Form (ICF) until the start of lixivaptan dosing. All other AEs and SAEs will be recorded from the start of lixivaptan dosing until exit from the study. Assessment windows are presented in [Table 12-2](#).

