7.6 Description of Subgroups to be Analyzed

No subgroup analyses are planned.

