28	4.1.2. – Exclusion criteria	15. Subjects with aspartate aminotransferase (AST), alanine aminotransferase (ALT), gamma-glutamyltransferase (GGT), alkaline phosphatase (ALP) or total bilirubin \geq 1.0 \times upper limit of normal (ULN) at Screening. Subjects with elevated	15. Subjects with aspartate aminotransferase (AST), alanine aminotransferase (ALT), gamma-glutamyltransferase (GGT), alkaline phosphatase (ALP) or total bilirubin $>$ 1.5 \times upper limit of normal (ULN) at Screening. Subjects with elevated	Increases the allowable upper limit of liver function test (LFT) results at Screening to 1.5 \times the upper limit of normal based on the observation in the first 8 subjects treated with

Page	Section	Version 4 dated January 9, 2019	Version 5	Comments
		bilirubin due to Gilbert's Syndrome may be allowed at the discretion of the Investigator.	bilirubin due to Gilbert's Syndrome may be allowed at the discretion of the Investigator.	lixivaptan at 200 mg BID (highest dose) in this study that no significant LFT abnormalities have been detected. The highest values were 1.2 times the upper limit of normal for transaminases with no increase in total bilirubin.
32	5.2 Blinding and Randomization	This is an open-label study and no blinding procedures will be used. Following enrollment, subjects will be centrally assigned to one of 4 cohorts depending on CKD status (Table 5 1) and based on a predetermined algorithm. The 200 mg BID dose cohorts will be enrolled first. At least 2 males or females will be included in the 8 subjects (i.e., can be up to a 25%/75% split of male/female or 75%/25% split of male/female) assigned to each cohort.	This is an open-label study and no blinding procedures will be used. Following enrollment, subjects will be centrally assigned to one of 4 cohorts depending on CKD status (Table 5 1) and based on a predetermined algorithm. The 200 mg BID dose cohorts will be enrolled first. At least 2 males or females will be included in the 8 subjects (i.e., can be up to a 25%/75% split of male/female or 75%/25% split of male/female) assigned to each cohort. Similarly, at least 2 subjects with CKD1 or CKD2 will be included in 8 subjects each assigned to Cohorts 1 and 3.	Provides for flexibility to stop enrollment of CKD1 subjects in Cohorts 1 and 3 if sufficient experience with CKD2 subjects has not occurred.

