# 7.4. EXAMINATION OF SUBGROUPS

Additional exploratory stratification will be made for summarizing some of the PK and/or PD endpoints, including:

- Male versus female (PK only)
- CKD1 versus CKD2 (within Cohorts 1 and 3)

Document: PK/PD STATISTICAL ANALYSIS PLAN
Author: [name]

Author: [name] Version Number: 1.0

Version Date: 12 Aug 2019

Template No: CS\_TP\_BS016 - Revision 5 Reference: CS\_WI\_BS005

Effective Date: 01Apr2018

Palladio BiosciencesInsert Customer Name/Logo PK/PD STATISTICAL ANALYSIS PLAN: PROTOCOL PA-102 Page 18 of 39

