### 14.1. PLASMA CONCENTRATION DATA

A listing of PK blood sample collection times as well as derived sampling time deviations will be provided. A subject listing of all concentration-time data will be presented. Presentation of individual sampling times/concentrations will be based on the Safety Analysis Set.

Lixivaptan and lixivaptan metabolite (WAY-141624, WAY-138451, and WAY-138758) plasma concentrations will be tabulated and summarized by analyte, cohort (equivalent to stratification by renal function/CKD stage and dose), Study Day, dosing interval (AM/PM), and nominal time point using descriptive statistics as described in Section 6.1 and Section 8. Additional summarization will be made with further stratification by gender (male versus female), and, independently, by CKD stage within cohort. Plasma concentrations that are below the lower limit of quantification (BLQ) will be treated as zero for the computation of summary statistics. Concentration summaries will be based on the PK Analysis Set.

The following plots will be presented for the concentration-time data:

- Arithmetic mean concentration versus time data (±SD) for Day 1 and Day 7 will be presented on linear and semi-logarithmic scales, stratified by analyte, cohort (equivalent to stratification by renal function/CKD stage and dose; and further stratified by CKD stage within cohort), Study Day, and dosing interval (AM/PM), based on the PK Analysis Set. Additional figure(s) will be made with further stratification by gender (male versus female).
- Arithmetic mean trough concentration versus nominal Study Day data (±SD) will be presented on a linear scale, stratified by analyte, cohort (equivalent to stratification by renal function/CKD stage and dose; and further stratified by CKD stage within cohort), and dosing interval (AM/PM), based on the PK Analysis Set. Additional figure(s) will be

PK/PD STATISTICAL ANALYSIS PLAN Document:

Author: [name] Version Number: 1.0 Version Date: 12 Aug 2019

Template No: CS\_TP\_BS016 - Revision 5 Reference: CS\_WI\_BS005

Effective Date: 01Apr2018

Palladio BiosciencesInsert Customer Name/Logo PK/PD STATISTICAL ANALYSIS PLAN: PROTOCOL PA-102 Page 23 of 39

made with further stratification by gender (male versus female).

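### The CKD-stage minimum for Cohorts 1 and 3 excludes no possible cohort, so as written it does not secure any CKD2 subjects

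*Protocol*

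**What the plan says.** Protocol 5.2 states that "at least 2 subjects with CKD1 or CKD2 will be included in 8 subjects each assigned to Cohorts 1 and 3". The footnote to Table 3-1 (Protocol 3.1) repeats the rule: "At least 2 subjects with CKD1 or CKD2 will be included in 8 subjects assigned to Cohorts 1 and 3".

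Entry to these two cohorts is limited to eGFR of at least 60 mL/min/1.73 m², labelled CKD1 or CKD2 (Table 3-1, inclusion criterion 4, Table 5-1). CKD3 subjects go to Cohorts 2 and 4.

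The stage rule in 5.2 opens with the word *Similarly* and follows a sex rule of the same form: "At least 2 males or females will be included in the 8 subjects". The sex rule is then explained by a permitted split of 25%/75% either way. The stage rule has no such explanation.

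The version 5 summary of changes gives the purpose of the stage rule: "Provides for flexibility to stop enrollment of CKD1 subjects in Cohorts 1 and 3 if sufficient experience with CKD2 subjects has not occurred". It is cited here only for purpose.

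The PK/PD SAP uses the stage split. Section 7.4 names CKD1 versus CKD2 within Cohorts 1 and 3 as an exploratory stratification. For PK, section 14.1 says "Additional summarization will be made with further stratification by gender (male versus female), and, independently, by CKD stage within cohort". For PD, section 15.1 says "Additional summarization will be made with further stratification CKD stage within cohort". Protocol 7.6, by contrast, says "No subgroup analyses are planned". Section 3.1 of the non-PK/PD SAP repeats the sex rule but not the stage rule.

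**The concern.** A minimum is useful only if some cohort could fail it. Here the condition for being counted is the same as the condition for entering the cohort, so the rule never restricts anything. A site or central assigner who follows the sentence exactly could fill Cohort 1 or Cohort 3 with 8 CKD1 subjects and comply. Nothing in the rule would ever tell them to stop taking CKD1 subjects, which is the action it was added to permit.

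What is at stake is limited. The planned CKD1 versus CKD2 summaries of PK and PD need subjects of both stages, and the text does not secure them. No primary summary depends on the split.

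**Working it through.** **1. Splits allowed by each reading.** Inputs: cohort size 8 (Tables 3-1 and 5-1) and two admissible stages. Let *k* be the number of CKD1 subjects and 8 − *k* the number of CKD2, with *k* = 0 to 8. That gives 9 splits.

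| Reading | Condition | Splits that qualify |
|---|---|---|
| As written | *k* + (8 − *k*) = 8 ≥ 2, always true | 9 of 9, including 8/0 and 0/8 |
| At least 2 of each stage | *k* ≥ 2 and 8 − *k* ≥ 2 | 5 of 9 (2/6 to 6/2) |
| At least 2 CKD2 | 8 − *k* ≥ 2 | 7 of 9 (0/8 to 6/2) |

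The first row is pure logic and needs no assumption about who presents at the sites.

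**2. What a two-sided minimum costs.** The documents give no stage mix, so this step rests on assumed mixes. Let *q* be the share of the rarer stage among eligible candidates, who arrive one at a time. Enrolment ends at the first candidate number, 8 or more, at which both stages have reached 2. Among the first 8 candidates, the chance of none of the rarer stage is P0 = (1 − *q*)^8, and the chance of exactly one is P1 = 8*q*(1 − *q*)^7. Each missing subject takes 1/*q* further candidates on average, so the expected number of candidates is 8 + (2·P0 + P1)/*q*, plus the same term for the commoner stage.

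- 50:50: P0 = 1/256 and P1 = 8/256. Each stage adds (10/256)/0.5 = 0.08. Total 8.16, or 8.2.
- 70:30: P0 = 0.0576 and P1 = 0.1977. The rarer stage adds 0.3129/0.3 = 1.04 and the commoner 0.002. Total 9.0.
- 80:20: P0 = 0.1678 and P1 = 0.3355. The rarer stage adds 0.6711/0.2 = 3.36 and the commoner almost nothing. Total 11.4.

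Subtracting 8, the average number of eligible subjects per cohort who find no slot is about 0.2, 1.0 and 3.4. The cost rises steeply with the imbalance: at 90:10 the same formula gives 20.4 candidates.

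**3. What a stratum of 2 would show.** PK/PD SAP 6.1 requires at least 3 observed values for descriptive statistics of a continuous variable. With exactly 2 it prints only the minimum and maximum. A minimum of 2 therefore puts both stages in the tables but does not guarantee a mean or SD for each.

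**4. Cohort size in Protocol 3.1.1 (editorial).** The plan's own figures reproduce at 8 per cohort:

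- Total: 4 × 8 = 32.
- Cmax: exp(±1.645 × √(0.086/8)) = 84.3% to 118.6%.
- AUC: exp(±1.645 × √(0.155/8)) = 79.5% to 125.7%.
- Chance of missing an AE of 10% incidence: 0.9^8 = 0.43.

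Section 3.1.1 instead gives 16 per cohort within a total of 32. Four cohorts of 16 would be 64, and the last figure would be 0.9^16 = 0.185. Sixteen is the number per CKD group, not per cohort.

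**The case against.** The strongest reply is that nobody would read the rule literally. The sex rule beside it has the same loose form, its 25%/75% split shows that 2 of each is meant, and *Similarly* carries that meaning across. Much of this stands, and it is why the point is low in severity. It does not remove the point. The Table 3-1 footnote lacks even the word *Similarly*, and the two clues to intent differ: the analogy with sex implies 2 of each stage, while the logged purpose speaks only of enough CKD2 experience.

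A second reply is that Protocol 3.1.1 expects no difference in PK or PD between CKD1 and CKD2 and pools them on purpose. That also stands. It makes the stage mix secondary, and with Protocol 7.6 it confirms that the stage summaries are exploratory.

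Third, assignment is central and follows a predetermined algorithm that is not in the documents. That algorithm may already apply the intended rule. A reader might infer from the wording that the cohorts did, or probably will, lack CKD2 subjects. The documents do not support that, since they give neither the algorithm nor the stage mix.

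A reader might also infer from the figure of 16 in 3.1.1 that the sample size is wrong. It is not: every calculation uses 8.

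**Conclusion.** The rule as written excludes no composition of Cohorts 1 or 3 (9 of 9 splits pass) and so cannot secure the CKD2 subjects for which it was added. This follows from the eligibility criteria alone. It is a low-severity correction to an operative enrolment rule. The cohort-level safety, PK and PD summaries and the stated precision are unaffected, and no actual imbalance is shown or claimed. Only the exploratory CKD1 versus CKD2 summaries are exposed, and in the extreme case they would have no CKD2 subjects to report.

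The candidate counts rest on assumed stage mixes and on candidates arriving independently. The 16-per-cohort figure in 3.1.1 is a clerical slip that changes no calculation.

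**What to change.** 1. In Protocol 5.2 and the Table 3-1 footnote, state the minimum by stage, for slots still open. For example: *Each of Cohorts 1 and 3 will include, among its 8 subjects, at least 2 with CKD1 and at least 2 with CKD2.* The sponsor should confirm that this is meant. If only the purpose in the change log was meant, the text should ask for at least 2 with CKD2. The central assignment algorithm should be checked against whichever is chosen.
2. Accept, or revisit, that a stage with exactly 2 subjects will show only a minimum and maximum under PK/PD SAP 6.1.
3. Editorial: in Protocol 3.1.1, give 8 subjects per cohort (16 per CKD group). Protocol 7.4 and both SAPs already use 8 and need no change.

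Total N is unchanged. The cost is a short amendment and possibly slower filling of the last slots, as worked above. The 200 mg cohorts enrol first, and the version 5 log reports 8 subjects already treated at 200 mg BID without saying how they divided between Cohorts 1 and 2. How many Cohort 1 slots the change could still affect is therefore unknown.
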